9.1.4 Discontinuation of the Patient from Study

Patients are free to withdraw from the study at any time without prejudice to further treatment. Patients who withdraw consent for further participation in the study will not receive any further IMP or further study assessments.

A patient who withdraws consent will always be asked about the reason(s) for withdrawal and the presence of any AEs. If a patient withdraws consent, they will be specifically asked if they are withdrawing consent for: all further participation in the study including any further follow-up (eg, telephone calls), and/or withdrawal of consent for the use of any samples.

9.2 End of Treatment and End of Study Procedures

At the EOS Visit (defined in Section 3.4), patients will undergo the procedures specified in the Schedule of Assessments. Following withdrawal for any reason, patients will attend an early termination visit and will undergo the procedures specified in the applicable Schedule of Assessments (Table 6-1, Table 6-2, Table 6-3 and Table 6-4), if possible. All data available for the patient at the time of withdrawal and all reasons for withdrawal, must be recorded in the eCRF.

9.3 Study Discontinuation

The Sponsor reserves the right to close the study site or terminate the study at any time for any reason at the sole discretion of the Sponsor. The study may be stopped if, in the judgment of the Sponsor, patients are placed at undue risk because of clinically significant findings that:

- Meet individual stopping criteria or are otherwise considered significant.
- Are assessed as causally related to study treatment.
- Are not considered to be consistent with continuation of the study.

Regardless of the reason for termination, all data available for the patient at the time of discontinuation of follow-up must be recorded in the eCRF. All reasons for discontinuation of treatment must be documented.

In terminating the study, the Sponsor will ensure that adequate consideration is given to the protection of the patients' interests.

Study sites will be closed upon study completion. A study site is considered closed when all required documents and study supplies have been collected and a study-site closure visit has been performed.

Reasons for the early closure of a study site by the Sponsor may include, but are not limited to, the following:

- Failure of the Investigator to comply with the protocol, the requirements of the IEC/IRB or local health authorities, the Sponsor's procedures, or GCP guidelines.
- Inadequate recruitment of participants by the Investigator.
- Discontinuation of further study intervention development.

9.4 Patient Replacement Policy

Patients who have been dosed will not be replaced.

Patients who are ineligible for study enrolment for reasons that are temporary, or who are unable to receive the first dose of study drug within the allowed Screening window for administrative reasons may be rescreened once after agreement to do so has been obtained in writing from the Medical Monitor.

[figure not shown]
10 STATISTICAL CONSIDERATIONS

An SAP based on the primary and secondary endpoints will be written and finalised before the study closure, ie, before database closure and unblinding of the randomisation code. The SAP will provide full details of the analyses, the data displays and the algorithms to be used for data derivations.

For all assessments, Baseline is defined as last recorded measurement prior to first IMP administration unless otherwise stated.

[figure not shown]
All safety and statistical programming, including PK analysis, will be conducted with Statistical Analysis System (SAS)[®] version 9.4 or higher for Windows (SAS Institute Inc., Cary, North Carolina, United States of America [USA]).

10.1 Sample Size Determination

10.2 Estimands and Intercurrent Event

10.3 Analysis Sets

10.3.1 Full Analysis Set

The full analysis set (FAS) includes all randomised patients. Efficacy analysis will be based on treatment allocated at randomisation which will be stratified by disease severity (moderate/severe) and region.

10.3.2 Safety Set

The safety set (SAF) will consist of all patients who take at least one dose of study treatment, including Placebo. Safety analysis will be based on actual treatment received.

10.3.3 Pharmacokinetic Set

The PK set will consist of all randomised and treated patients in the SAF with a Baseline assessment and at least one post-Baseline PK sample (with adequate documentation of dosing and sampling dates and times).

10.3.4 Anti-drug Antibody Set

The ADA set will consist of all randomised and treated patients in the SAF with a Baseline ADA result (positive, negative or inconclusive) and at least one post-Baseline ADA result (positive, negative or inconclusive).

10.4 Statistical Analyses

Full details of the statistical analyses of the data will be documented in an agreed SAP, which will be finalised prior to locking the database. Analyses will be performed by treatment regimen.

For continuous variables, descriptive statistics will include: the number of patients, mean, median, SD, minimum, and maximum.

For categorical or ordinal data, frequencies and percentages will be displayed for each category.

10.4.1 Demographic and Baseline Characteristics

Demographic variables (age, gender and ethnicity) and medical history (coded according to the Medical Dictionary for Regulatory Activities [MedDRA]) will be summarised by treatment regime for FAS and SAF. Body weight, height and BMI will also be summarised by treatment regimen.

10.4.2 Efficacy Analysis

An overall test for the treatment effect of KY1005 will be conducted. Pairwise comparisons of each KY1005 treatment group versus Placebo group will be performed.
For the continuous endpoints
An analysis of covariance (ANCOVA) model will be used. This model includes treatment, randomisation strata (region, disease severity) as fixed effects, and baseline value as a covariate.
Covariate.
A mixed-effect model with repeated measures (MMRM) will be used as a sensitivity analysis for primary and continuous key secondary endpoints. This model includes the factors (fixed effects) for treatment, randomisation strata (region, disease severity), visit, treatment-by-visit interaction, and relevant baseline value. Within the framework of MMRM, the treatment difference will be tested at the pre-specified primary timepoint, Day 113 (Week 16), as well as at the other timepoints by timepoint-specific contrasts from the MMRM model.
For the categorical endpoints
Cochran-Mantel-Haenszel test stratified by randomisation strata (region, disease severity) will be used at the analysis timepoint.

Other sensitivity analysis might be performed and details will be specified in the SAP.

Data will be presented graphically, where applicable, and with summary statistics by visit and by treatment regimen.

[figure not shown]

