	• Percentage of patients with at least a 75% reduction from Baseline in EASI (EASI 75) at Days 113 (Week 16) and 169 (Week 24).		
	• Percentage of patients with a response of IGA 0 or 1 and a reduction from Baseline of ≥2 points at Days 113 (Week 16) and 169 (Week 24).		
	• Proportion of patients with improvement (reduction) of weekly average of pruritus NRS ≥4 with a Baseline pruritis NRS of ≥4 from Baseline to Days 113 (Week 16) and 169 (Week 24).		
	Other secondary efficacy endpoints:		
	• Absolute change from Baseline in EASI at Days 15 (Week 2), 29 (Week 4), 57 (Week 8), 85 (Week 12), 113 (Week 16), 141 (Week 20) and 169 (Week 24).		
	• Percentage change from Baseline in EASI at Days 15 (Week 2), 29 (Week 4), 57 (Week 8), 85 (Week 12) and 141 (Week 20).		
	• Percentage of patients with at least a 50% reduction from Baseline in EASI (EASI 50) at Days 15 (Week 2), 29 (Week 4), 57 (Week 8), 85 (Week 12), 113 (Week 16), 141 (Week 20) and 169 (Week 24).		
	• Percentage of patients with at least a 75% reduction from Baseline in EASI (EASI 75) at Days 15 (Week 2), 29 (Week 4), 57 (Week 8), 85 (Week 12) and 141 (Week 20).		
	• Percentage of patients with at least a 90% reduction from Baseline in EASI (EASI 90) at Days 15 (Week 2), 29 (Week 4), 57 (Week 8), 85 (Week 12), 113 (Week 16), 141 (Week 20) and 169 (Week 24).		
	• Percentage of patients with a 100% reduction from Baseline in EASI (EASI 100) at Days 15 (Week 2), 29 (Week 4), 57 (Week 8), 85 (Week 12), 113 (Week 16), 141 (Week 20) and 169 (Week 24).		
	• Change in IGA from Baseline to Day 113 (Week 16) and over time.		
	• Percentage of patients with a response of IGA 0 or 1 and a reduction from Baseline of ≥2 points at Days 15 (Week 2), 29 (Week 4), 57 (Week 8), 85 (Week 12) and 141 (Week 20).		

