An overall test for the treatment effect of KY1005 will be conducted. For each treatment regimen and all efficacy variables, the analysis will be comparisons of each of the KY1005 treatment groups with the Placebo group. For the primary endpoint, the overall type I error rate will be controlled using a hierarchical testing procedure across the four dose regimens against placebo. For each secondary endpoint analyzed, the same multiplicity adjustment approach will be applied as for the primary endpoint. No multiplicity adjustment will be made across the endpoints.

1-Mar-2022

Version number: 1

For the continuous endpoints: An analysis of covariance (ANCOVA) model will be used. This model includes treatment, randomisation strata (region, disease severity) as fixed effects, and baseline value as a covariate.

A mixed-effect model with repeated measures will be used as a sensitivity analysis for primary and continuous key secondary endpoints. This model includes the factors (fixed effects) for treatment, randomisation strata (region, disease severity), visit, treatment-by-visit interaction, and relevant baseline value.

For the categorical endpoints: Cochran-Mantel-Haenszel test stratified by randomisation strata (region, disease severity) will be used at each analysis timepoint.

Data will be presented graphically, where applicable, and with summary statistics by visit and by treatment regimen.

Safety Analyses:

Adverse events will be coded using the Medical Dictionary for Regulatory Activities (MedDRA, latest version) and will be summarised in incidence tables by System Organ Class and Preferred Term, and by treatment regimen. Adverse events will be further summarised by maximum severity and relationship to study medication. Concomitant medications will be coded using the World Health Organization Drug Dictionary and will be summarised in incidence tables by Drug Class and Preferred name, and by treatment regimen.

Other routine safety assessments such as vital signs, 12-lead ECG and safety laboratory tests will be summarised by treatment regimen using statistics for continuous or categorical data, as appropriate.

Pharmacokinetic Analyses:

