4.2 Inclusion Criteria

Patients must fulfil all the following inclusion criteria for entry into the study:

- 1. Adults (18 to <75 years of age) with AD as defined by the American Academy of Dermatology Consensus Criteria [Eichenfield et al., 2014] for 1 year or longer at Baseline (Day 1; prior to first administration of IMP). For United Kingdom, see Section 17.15.2 (Appendix 15).
- 2. EASI of 12 or higher at the Screening Visit and 16 or higher at Baseline.
- 3. IGA of 3 or 4 at Baseline.
- 4. AD involvement of 10% or more of body surface area (BSA) at Baseline.
- 5. Baseline worst/maximum pruritus NRS of ≥4. The baseline weekly average of daily worst/maximum pruritus NRS will be calculated from the 7 consecutive days immediately preceding the Baseline visit. A minimum of 4 daily scores out of the 7 will be required.
- 6. Documented history, within 6 months prior to Baseline, of either inadequate response or inadvisability of topical treatments.

a) Acceptable documentation includes contemporaneous chart notes that record TCS/TCI prescription and treatment outcome, or Investigator documentation based on communication with the patient's treating physician.

1-Mar-2022

[figure not shown]
Version number: 1

- b) Failure to achieve and maintain remission or low disease activity (eg, IGA 0, clear skin to 2, mild disease) despite treatment with TCS of medium to high potency (± topical calcineurin inhibitor as appropriate), applied daily for at least 28 days or for the maximum duration recommended by the product prescribing information (eg, 14 days for super-potent TCS), whichever was shorter. NOTE: Patients who failed systemic therapies intended to treat AD within 6 months preceding screening, such as cyclosporine, methotrexate, azathioprine, and mycophenolate will be also considered as surrogate for having inadequate response to topical therapy. Washout of prior systemic medications must be completed as per the protocol requirements.
- c) Important side effects or safety risks defined as those that outweigh the potential treatment benefits including (but not limited to) hypersensitivity reactions, significant skin atrophy, treatment intolerance and adverse systemic effects, as assessed by the investigator or treating physician.
- 7. Must have applied a stable dose of topical bland emollient (simple moisturiser, no additives [eg, urea]) at least twice daily for a minimum of 7 consecutive days before Baseline.

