### 2.3. Exploratory Objectives and Endpoints

## 3. Investigational Plan

### 3.1. Overall Study Design and Plan

This is a Phase IIb, randomised, double-blind, placebo-controlled, parallel group, multicentre dose ranging study to characterise the efficacy and safety of SC administered KY1005 in adult patients with moderate-to-severe AD who have a documented history, within 6 months prior to Baseline, of an inadequate response to, or inadvisability of, topical treatments.

Patients who continue to meet the eligibility criteria at Baseline will be randomised 1:1:1:1:1 to receive a SC dose of KY1005, or matching Placebo. The randomisation will be stratified by disease severity (moderate/ severe) and region at baseline. Disease Severity at baseline is defined as moderate (Baseline EASI  $\leq$  21) and severe (Baseline EASI  $>$ 21). Up to 350 patients (approximately 70 patients per treatment arm) will be enrolled.

Four different SC KY1005 dosing regimens will be tested versus Placebo. From Baseline up to Day 169 (Week 24), investigational medicinal product (IMP) will be administered at the following doses and intervals; 500 mg loading dose (given as [redacted] SC administration) followed 28 days later and thereafter with 250 mg every 4 weeks (Q4W) or the following regimens from Baseline: 250 mg Q4W, or 125 mg Q4W or 62.5 mg Q4W or Placebo Q4W.

At Baseline those patients not receiving a KY1005 loading dose will receive both KY1005 and Placebo to maintain the study blind. All patients will therefore receive [REDACTED] SC doses at Baseline.

To enable Placebo patients and those patients randomised to the KY1005 62.5 mg Q4W, 125 mg Q4W and 250mg Q4W treatment arms to receive KY1005 at a dose expected to elicit a meaningful clinical response (based on prior clinical evidence), patients who do not achieve  $\geq$  EASI 75 or IGA 0/1 at Week 24 will be invited to enroll in the LTE study (LTS17367) where they will receive KY1005.

[figure not shown]

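### The CMH test for the binary key secondary endpoints leaves out baseline itch: a small loss of power, mainly for the NRS ≥4 responder endpoint, that is cheap to recover

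*Protocol*

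**What the plan says.** For categorical endpoints, Protocol 10.4.2 specifies a "Cochran-Mantel-Haenszel test stratified by randomisation strata (region, disease severity"). The synopsis has the same test: "Cochran-Mantel-Haenszel test stratified by randomisation strata (region, disease severity) will be used at each analysis timepoint". The severity factor is an EASI cut. The definition in SAP 3.1 begins "Disease Severity at baseline is defined as moderate (Baseline EASI" and puts moderate at 21 or below and severe above 21.

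Continuous endpoints are treated differently. There the ANCOVA carries the strata and also the baseline: "This model includes treatment, randomisation strata (region, disease severity) as fixed effects, and baseline value as a covariate".

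The itch endpoint is "Proportion of patients with improvement (reduction) of weekly average of pruritus NRS ≥4 with a Baseline pruritis NRS of ≥4", at Weeks 16 and 24. Protocol 4.2 makes both relevant baselines entry criteria: "Baseline worst/maximum pruritus NRS of ≥4", from at least four of seven daily scores, and "IGA of 3 or 4 at Baseline". In the visible SAP text, IGA 3 v 4 appears as a subgroup factor (4.4.5), but no baseline covariate is named for the binary tests. SAP Table 4, which covers these endpoints, is redacted. Protocol 10.4.2 leaves room for further sensitivity analyses in the SAP.

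**The concern.** The plan adjusts EASI percentage change for baseline EASI on top of the severity stratum, but it does not adjust itch response for baseline itch. An absolute fall of 4 points depends on the starting value by construction: from 4 it means complete clearance of itch, from 8 it means halving. IGA 0/1 likewise needs a 2-point fall from IGA 3 and a 3-point fall from IGA 4. A two-level EASI cut is at best an indirect proxy for baseline itch.

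What is at stake is power, most of all for itch. At phase 2a rates itch has the lowest power of the binary key secondary endpoints. By the synopsis, each secondary endpoint also goes through the hierarchical procedure over four doses, so within that endpoint a missed dose stops the later tests.

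**Working it through.** **1. The plan's own figure.** No power is stated for any binary endpoint. The synopsis figure of at least 84% is for the primary endpoint, and its planning difference and SD are not visible. The phase 2a high-dose difference, 69.97 − 49.37 = 20.60, with SD 41 gives 83.9% by t-test at 70 per arm. The 84% is thus plausible but cannot be confirmed, and it does not bear on this point.

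**2. Starting power.** Rates are from Protocol Table 1-1. For two proportions, power = Φ[(δ − 1.96·√(2p̄(1−p̄)/n)) / √((p₀(1−p₀) + p₁(1−p₁))/n)], with n = 70.
- Itch 38.1% v 57.9%: (0.198 − 1.96 × 0.0845)/0.0828 = 0.39, power 65.3% (50.1% at the 49 completers per arm assumed in Protocol 3.6).
- Itch 38.1% v 62.5%: (0.244 − 1.96 × 0.0845)/0.0820 = 0.96, power 83.0%.
- IGA 0/1 8.3% v 37.0%: (0.287 − 1.96 × 0.0708)/0.0665 = 2.23, power 98.7%.
- EASI 75 25.0% v 51.9%: 91.4%.

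**3. Simulation design.** Two arms of 70, 12,000 trials per case, six strata (three regions × two severities). The comparison is CMH, then a logistic score test on the same strata, then the same score test with baseline added. The score statistic was multiplied by √((N−k)/N), where N = 140 and k is the number of model parameters including treatment. This held type I error at 4.5–4.9%. Simulation error per power figure is about √(0.64 × 0.36/12,000) = 0.4 points.

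Assumptions not in the documents: regions 25/50/25; 60% severe; baseline NRS mean 7.5, SD 1.5, correlation 0.3 with severity; IGA 4 in 50% of severe and 15% of moderate patients; prognostic strength varied.

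**4. Itch, 38.1% v 57.9%, power in %.**

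| Baseline effect | CMH | Logistic, strata | + baseline NRS | Share due to baseline |
|---|---|---|---|---|
| OR per SD 1.0 | 63.9 | 64.0 | 63.7 | −0.3 |
| OR 1.5 | 64.2 | 64.7 | 65.3 | 0.6 |
| OR 2.0 | 63.7 | 64.3 | 67.2 | 2.9 |
| OR 2.5 | 63.8 | 64.0 | 69.7 | 5.7 |
| Proportional fall, SD 0.45 (OR 1.49) | 63.9 | 64.2 | 65.6 | 1.4 |
| Proportional fall, SD 0.35 (OR 1.72) | 64.4 | 64.8 | 66.9 | 2.1 |
| Proportional fall, SD 0.25 (OR 2.09) | 65.2 | 65.8 | 69.8 | 4.0 |

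If itch falls in proportion to baseline, the responder definition alone implies an OR of about 1.5 to 2.1, so the OR 2.5 row lies beyond that range. At 38.1% v 62.5%, CMH to baseline-adjusted power is 81.5 to 82.4% (OR 1.5) and 82.3 to 85.2% (OR 2.0).

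**5. Five-arm model.** A five-arm Wald test (3,000 trials) raised power from 62.2–63.2% to 66.4–67.8% at 38.1% v 57.9%. About 1.5 points came from the change of test and about 2 to 4 from baseline NRS. Type I error was 5.3–5.7%, against about 5.1% for CMH.

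**6. Treatment failure.** Protocol 5.3.4 counts topical rescue as failure. With assumed failure of 30% on placebo and 20% on active, and overall response held at 38.1% v 60% (Table 1-1 pooled active: 26/43 = 60.5%), adding NRS to the five-arm logistic model gained, at reduction SD 0.25 and 0.35:
- failure unrelated to baseline: 2.2 and 1.2 points;
- log-odds of failure +0.4 per SD of NRS: 0.9 and 0.0;
- log-odds +0.7 per SD: 0.3 and 0.1.

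**7. IGA 0/1, CMH to logistic with baseline IGA.** At 8.3% v 37.0%: 98.8 to 99.0% (OR 0.33 for IGA 4 v 3). At an assumed 8.3% v 25%: 76.3 to 76.6% (OR 0.5), 76.4 to 77.2% (0.33), 76.8 to 78.7% (0.2).

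**8. Baseline itch as a further CMH stratum (12 strata).** At 38.1% v 57.9%: 63.8 to 62.7% (OR 1.5), 63.9 to 63.6% (2.0), 64.1 to 66.0% (2.5).

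**The case against.** A CMH test on the randomisation strata is valid, needs no outcome model and kept type I error at 4.7–5.1% in these simulations. Using it is a defensible choice, and that stands.

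The size of the gain is also uncertain. Rescue is given for intolerable symptoms, so patients with high baseline itch may fail more often, which offsets their arithmetic advantage. Step 6 shows that this can remove the gain. It stands as a reason to quote a range that starts at zero.

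Three stronger readings are tempting, and the documents do not support them:
- A reader might infer that power is lost across itch, IGA and EASI 75 alike. At the Table 1-1 high-dose rate IGA has nothing useful to gain. IGA is graded on erythema and papulation, which are also EASI signs, so the severity stratum is not unrelated to it. For EASI 75 the stratum is a two-level form of its own baseline, and no loss has been shown.
- A reader might credit the whole gap between CMH and a five-arm logistic model to baseline itch. Part of it comes from changing the test. An uncorrected score test gained 2.0 points (63.8 to 65.8%) even with no baseline effect at all.
- A reader might infer that one miss halts all secondary testing. The synopsis makes no adjustment across endpoints, so a miss stops only the later doses for that endpoint.

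Finally, the SAP wording for these endpoints is redacted. A covariate there cannot be excluded, so the point is shown for the protocol text only.

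**Conclusion.** The point holds as a cheap improvement, mainly for the itch responder endpoint. As the protocol is written, baseline NRS is collected in every patient and left out of a test whose outcome depends on it. At 70 per arm and phase 2a itch rates, using it is worth roughly 0 to 4 points of power. The gain is about 2 to 4 points over most of the proportional-fall settings (1.4 at the weakest) and near 0 if rescue or other failure rises with baseline itch. For IGA 0/1 it is negligible at the phase 2a high-dose rate and about 0 to 2 points at 8.3% v 25%.

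These sizes rest on an assumed baseline NRS distribution, stratum mix and prognostic strength, none of which the documents give. The planned analysis is not in error.

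**What to change.** Before unblinding, pre-specify for NRS ≥4 at Weeks 16 and 24 a logistic regression on all five arms with treatment, region, severity stratum and continuous baseline NRS. Report the standardised (marginal) risk difference v placebo with a robust 95% CI, so that the quantity estimated stays a difference in proportions. Test with a df-corrected score test or similar, because a plain Wald test ran slightly above 5%. Keep the stratified CMH test as sensitivity analysis. Baseline IGA (3/4) may be added to an IGA model in the same way. Do not add baseline as a further CMH stratum, which gives little or no gain.

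The cost is SAP wording, some programming (standardisation within each imputed dataset where imputation is used) and mild model dependence, which the retained CMH test covers. No extra patients or visits are needed. If SAP Table 4 already includes these covariates, nothing need change.
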